**(6) Distant Metastasis Rate (%)**

The percentage of patients with distant metastasis among the total study population.

**(7) Distant Metastasis-Free Survival (DMFS)**

The time interval (in months) from the date of initial surgery to the date of first distant metastasis. Patients without metastasis are censored at the date of last follow-up.

**(8) Cumulative Metastasis Rate**

The cumulative probability of distant metastasis at 1, 3, 5, and 10 years after surgery.

**(9) Overall Survival (OS)**

The time interval (in months) from the date of initial surgery to the date of death from any cause. Surviving patients are censored at the date of last follow-up.

**(10) Overall Survival Rate**

The cumulative probability of survival at 1, 3, 5, and 10 years after surgery, estimated by the Kaplan-Meier method.

**(11) Median Survival Time**

The time point (in months) after surgery at which 50% of patients are still alive, estimated from the Kaplan-Meier survival curve.

**3.2.2 Secondary Endpoints and Definitions**

**(1) Age at diagnosis** – Age (in years) when the patient was first diagnosed with breast PT.

- (2) **Menstrual status** – Premenopausal or postmenopausal.
- (3) **Childbirth history** – Yes or no.
- (4) **Family history of malignant tumors and PT** – Includes family history of breast cancer, other malignant tumors, and PT. Categorized as yes or no.
- (5) **Previous fibroadenoma surgery** – History of breast surgery for fibroadenoma. Categorized as yes or no.
- (6) **Maximum tumor diameter** – Largest tumor dimension (in cm) measured by preoperative imaging (ultrasound, etc.).
- (7) **Multifocality** – Solitary or multiple ( $\geq 2$  lesions in the same breast).
- (8) **Tumor location** – Left breast, right breast, or bilateral.
- (9) **Imaging findings** – Descriptions from breast and axillary ultrasound, mammography, breast MRI, chest CT, PET-CT, etc. (e.g., lobulated shape, margins, vascularity).
- (10) **Histological grade** – Benign, borderline, or malignant according to WHO criteria.
- (11) **Surgical procedure** – Type of initial surgery: wide local excision, total mastectomy, mastectomy with reconstruction, breast-conserving surgery, etc.
- (12) **Margin status** – Whether tumor cells are present at the surgical margin on postoperative pathology: negative (no residual tumor) or positive (residual tumor present). Margin distance (in cm) is also recorded.
- (13) **Adjuvant chemotherapy** – Whether adjuvant chemotherapy was given after surgery (yes/no), with details of regimen if available.
- (14) **Adjuvant radiotherapy** – Whether adjuvant radiotherapy was given after surgery (yes/no), with details of regimen if available.
- (15) **Axillary biopsy report** – Whether axillary lymph node biopsy (sentinel lymph node biopsy or axillary lymph node dissection) was performed, and the total number of lymph nodes examined and number of positive nodes recorded.

### **3.2.3 Secondary Endpoints – Categorized**

- (1) **Demographic characteristics** – Age at diagnosis, menstrual status, childbirth history, family history of malignant tumors/PT, previous fibroadenoma surgery, history of other malignant tumors (excluding breast cancer).

(2) **Tumor characteristics** – Maximum tumor diameter, multifocality, tumor location, imaging findings, histological grade.

(3) **Treatment modalities** – Surgical procedure, margin status, chemotherapy (yes/no), radiotherapy (yes/no), axillary biopsy report.

## **4. Study Population**

### **4.1 Inclusion Criteria**

(1) Patients with a postoperative paraffin-embedded pathology diagnosis of breast phyllodes tumor (benign, borderline, or malignant) according to WHO criteria.

(2) Patients who underwent surgical treatment at any participating center during the designated time period.

(3) Patients with complete or reasonably complete clinical records, pathology reports, and follow-up data sufficient to extract the core variables required by the study protocol.

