#### **3.2 Study Endpoints**

##### **3.2.1 Primary Endpoints and Definitions**

###### **(1) Local Recurrence (LR)**

Local recurrence is defined as a pathologically confirmed reappearance of PT in the ipsilateral breast, chest wall, or axillary lymph nodes after initial surgery. Diagnosis is confirmed by postoperative follow-up records (outpatient visits, hospital admissions, imaging findings) and pathology reports.

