###### **(2) Local Recurrence Rate (%)**

The percentage of patients with local recurrence among the total study population.

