**(3) Recurrence-Free Survival (RFS)**

The time interval (in months) from the date of initial surgery to the date of first pathologically confirmed local recurrence. Patients without recurrence are censored at the date of last follow-up.

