## **5. Study Design**

### **5.1 Overall Design**

[figure not shown]
This is a multicenter, retrospective cohort study. Data will be collected from patients who underwent breast surgery at the Departments of Breast Surgery of the following eight participating centers between January 1, 2001, and December 31, 2023:

- Sun Yat-sen Memorial Hospital, Sun Yat-sen University
- The First People's Hospital of Foshan
- Sun Yat-sen University Cancer Center
- Peking University Shenzhen Hospital
- Foshan Women and Children's Hospital
- The First Affiliated Hospital of Guangzhou Medical University
- Zhongshan People's Hospital
- Shanwei People's Hospital

The expected sample size is approximately 3,500 patients. Using real-world data over nearly 20 years, the study will systematically describe the clinicopathological characteristics, treatment patterns, and long-term prognosis of breast PT in China, and identify independent risk factors through descriptive analysis, propensity score methods, competing risk models, and sensitivity analyses.

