5.2 Study Flow Diagram

### 5.3 Methods to Reduce Bias

(1) **Standardized data collection** – All data extractors at participating centers will receive uniform training. Standardized Case Report Forms (CRFs) will clearly define each variable (e.g., “positive margin” defined as tumor cells present at the margin on pathology; “local recurrence” requires pathological confirmation) to reduce measurement and information bias.

(2) **Double independent extraction of key variables** – For primary outcome variables (recurrence, metastasis, death) and key exposure variables (pathological grade, surgical procedure, margin status), two researchers will independently extract data and cross-validate. Discrepancies will be adjudicated by a third senior researcher.

(3) **Clear inclusion/exclusion criteria** – Strict definitions will avoid selection bias. All eligible consecutive cases will be enrolled; no sampling based on outcome or exposure.

(4) **Handling of missing data** – Cases with >20% missing key variables will be excluded. For variables with  $\leq 20\%$  missingness, multiple imputation ( $m=5$ ) will be used. Results from complete case analysis and imputed analysis will be compared to assess missingness bias.

(5) **Confounding control** – Multivariable regression models will adjust for known prognostic factors (age, tumor size, pathological grade, margin status, etc.). For non-randomized treatment comparisons (e.g., different surgical procedures), propensity score matching (PSM, caliper =  $0.2 \times \text{SD of PS}$ ) or inverse probability of treatment weighting (IPTW) will be used to balance covariates. E-values will be calculated to evaluate the strength of unmeasured confounding.

(6) **Control of multicenter heterogeneity** – Center effects will be adjusted using Cox shared frailty models or generalized estimating equations (GEE) with center as a random effect.

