## **6.2 Data Management**

### **6.2.1 Data Anonymization**

All extracted data will be stripped of direct identifiers such as name and ID number, and will only be identified by a study number. Data access will be restricted to the principal investigator and designated data analysts.

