### **6.2.4 Database Establishment and Management Methods**

The database will contain multiple interrelated tables, such as: patient basic information table, diagnosis information table, surgical treatment table, pathological characteristics table, follow-up information table, and molecular biomarker results table. All tables will be linked through a unique medical record number.

- **Variable Definition:** A detailed Data Dictionary will be developed to clearly define each variable in the eCRF (including variable name, type, value meaning, unit, source of collection, etc.), ensuring consistent understanding among all research personnel.
- **Blinding:** Data entry personnel will be blinded to patients' final follow-up outcomes (whether recurrence/metastasis occurred) during the entry of clinical and pathological data, to avoid introducing subjective bias at the data entry stage.
- **Quality Monitoring:** Regular centralized monitoring of data quality will be performed, with reports on outliers, logical errors, data consistency, and data entry progress.
- **Database Lock:** After final data cleaning, verification, and confirmation, the database will be formally locked, and any unauthorized modifications will be prohibited. Any request to modify locked data must be approved by the principal investigator, with detailed documentation of the reason, content, and date of modification, and the locking process will need to be repeated. The data lock for this study is planned to occur once, just before the formal statistical analysis begins.

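### Entry does not require the first phyllodes operation to be at a participating centre, and initial surgery is undefined, so recurrence estimates rest on outcome-dependent entry or a wrong time zero

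*Combined protocol and SAP*

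**What the plan says.** Section 4.1, inclusion criterion (2), admits "Patients who underwent surgical treatment at any participating center during the designated time period". Section 5.1 describes the source in the same terms: "Data will be collected from patients who underwent breast surgery at the Departments of Breast Surgery of the following eight participating centers", with a window of 1 January 2001 to 31 December 2023. Nothing in 4.1 or 4.2 requires that operation to be the first for PT, and nothing excludes a woman whose tumour at the centre is already a recurrence.

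The endpoints in section 3.2.1 are built on a first operation:

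- LR: "Local recurrence is defined as a pathologically confirmed reappearance of PT in the ipsilateral breast, chest wall, or axillary lymph nodes after initial surgery".
- Crude LR rate: "The percentage of patients with local recurrence among the total study population".
- Recurrence-free survival (RFS): "The time interval (in months) from the date of initial surgery to the date of first pathologically confirmed local recurrence".
- Distant metastasis-free survival and overall survival use the same origin.

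Initial surgery is not defined as either the first PT operation anywhere or the first at a participating centre. Sections 3.2.2 and 3.2.3 list previous fibroadenoma surgery, but neither previous PT surgery nor primary versus recurrent status. Section 5.3 (3) states "All eligible consecutive cases will be enrolled; no sampling based on outcome or exposure". Section 5.4.2 plans Kaplan-Meier, Cox, cumulative incidence and Fine-Gray analyses without delayed entry, and none of its sensitivity analyses separates primary from recurrent presentation.

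**The concern.** The eight centres are tertiary hospitals, and one is a cancer centre. Some women may arrive there for re-operation after PT surgery elsewhere. The documents do not say how many, but criterion (2) lets them in.

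Take the first PT operation anywhere as time zero. A woman referred with a pathologically confirmed recurrence is then in the cohort only because she recurred. A woman operated on at the same outside hospital who never recurred has no route in. That is entry conditional on the outcome, which the statement in 5.3 (3) is meant to rule out. The referred woman also contributes event-free time from before she could have been observed (left truncation).

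Take the first operation at the centre instead. Her recurrence then becomes the index tumour, and her clock starts at the wrong point in the disease.

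Either way, the first-listed primary endpoint, the time-to-recurrence description and the prognostic-factor models for LR are affected. Because the status variable is not listed, the analyst could not reliably identify these women after database lock.

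**Working it through.** **Inputs from the documents.** Expected N = 3,500, grade mix 7:2:1, overall recurrence about 11%, about 380 events, 30–40 model variables (section 5.4.1). Grade-specific recurrence 7.1%, 16.7% and 25.1% (section 2.2.2).

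**Input not in the documents.** f, the share of the cohort that enters through re-operation for a recurrence after outside PT surgery. It is an assumption, shown from 1% to 10%.

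**1. The plan's own figure.** 3,500 × 0.11 = 385. Grade-weighted: 0.7 × 7.1% + 0.2 × 16.7% + 0.1 × 25.1% = 10.82%, and 3,500 × 0.1082 = 378.7. Both reproduce about 380.

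**2. First reading (first PT operation anywhere).** Each referred woman is an event by definition. With p = 10.82% among women whose first PT operation was at a centre:

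observed crude LR = (1 − f) × p + f

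share of events fixed at entry = f / observed crude LR

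| Assumed f | Women entering this way | Observed LR | LR events | Fixed at entry |
|---|---|---|---|---|
| 0% | 0 | 10.8% | 379 | 0% |
| 1% | 35 | 11.7% | 410 | 8.5% |
| 2% | 70 | 12.6% | 441 | 15.9% |
| 5% | 175 | 15.3% | 535 | 32.7% |
| 10% | 350 | 19.7% | 691 | 50.7% |

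The slope is 1 − p = 0.89, so each 1% of the cohort adds about 0.9 percentage points. The direction is the same for the Kaplan-Meier and cumulative incidence estimates, because the women who would balance these events are missing from the risk sets.

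**3. Second reading (first operation at the centre).** The formula does not apply, because a referred woman is not an event at entry. Two populations are pooled with time zero at different stages of disease. The effect depends on how later recurrence risk differs between them, and the documents give no figure for that.

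**4. Do other provisions close the gap?**

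- Inclusion (3), exclusion (3) and the 20% missing-data rule in 5.3 (4) act on record completeness. They may drop some referred women, but not those with good outside records.
- Exclusion (2) concerns prior malignant tumours, so it would not reach prior benign or borderline PT.
- The logic check in 6.2.3 (surgery not later than recurrence) passes if the outside surgery date is entered. It flags the record only if the centre date is used together with the earlier recurrence.
- Dropping follow-up under 6 months does not target these women. On the first reading their clock starts at the outside operation.
- Centre frailty or GEE in 5.3 (6) adjusts between-centre differences and cannot undo outcome-dependent entry.

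**The case against.** The strongest reply is that this is an ambiguity and not a demonstrated bias. All data come from the centres' own systems (section 6.1.2), so initial surgery may well mean the first operation there, and then no one is an event at entry. The completeness rules would remove some women first treated elsewhere, because surgical procedure is defined as the type of initial surgery and patients missing it are excluded. The abstract refers to PT diagnosed from 2001 to 2023, which counts against very early outside operations. The flow diagram is not reproduced in the text available, so it could not be checked. The referral share has no source.

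Much of this stands. It limits the size and makes the upward bias conditional on one reading. It does not remove the defect: the other reading still mixes primary and recurrent disease, and no criterion restricts entry to a first operation at a centre.

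A reader might also infer three stronger things that the documents do not support:

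- **Distant metastasis is inflated too.** A woman referred for local recurrence is not thereby a metastasis event, and nothing in the plan quantifies such an effect.
- **The grade mix shifts towards malignant disease.** The plan gives no grade distribution for referred patients.
- **Cross-centre duplicates add to the inflation.** Section 6.2.4 says "All tables will be linked through a unique medical record number" and 6.2.1 says "All extracted data will be stripped of direct identifiers such as name and ID number". Double counting follows only if record numbers are hospital-specific, which is not stated. Matching before identifiers are removed is not ruled out. If it did happen, one woman with a recurrence would appear as two women without one, which lowers LR.

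**Conclusion.** The point holds in conditional form. As written, the plan yields either outcome-dependent entry with upward bias in LR, or a cohort mixing primary and recurrent disease with a wrong time zero. Which one applies turns on a term that the protocol leaves undefined. On the first reading the bias is about 0.9 percentage points of crude LR per 1% of the cohort. This assumes that LR is 10.8% among women first operated on at a centre, that N stays at 3,500, and that every referred woman is retained. Completeness exclusions would make it smaller. The referral share is unknown, so the table shows sensitivity and is not an estimate. The matter should be settled before data extraction, because the status variable needed to separate these women is not among those listed.

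**What to change.** 1. Restrict the primary LR, distant metastasis and overall survival analyses to patients whose first PT excision took place at a participating centre between 1 January 2001 and 31 December 2023, and define initial surgery as that excision.
2. Add eCRF fields for place and date of first PT surgery and for primary or recurrent status at the centre operation.
3. State how non-recurrent women referred for early completion re-excision after an outside excision are handled, for example with delayed entry at the centre operation. A restriction with no such rule would remove them although they have not recurred.
4. Report women presenting with recurrence as a separate descriptive group, or include them in a sensitivity analysis with delayed entry at the centre operation and only later events counted.
5. As a secondary check, confirm whether medical record numbers are unique across the eight centres. If they are not, de-duplicate before identifiers are removed.

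**Cost.** Protocol and SAP wording, a few eCRF fields, and ethics committee approval of the amendment (section 7). Some of the projected 3,500 patients and about 380 events leave the primary analysis. If the planned 385 events (11%) already included women entering through recurrence, removing them would leave 385 − 3,500f events: 350, 315 or 210 at f = 1%, 2% or 5%. At 210 events, 30–40 variables would have 7.0 to 5.3 events each (210/30, 210/40), against 12.7 to 9.5 at 380 (380/30, 380/40). The model-size statement in 5.4.1 should therefore be rechecked once primary/recurrent status is known.

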### **4.2 Exclusion Criteria**

(1) Patients with a postoperative pathological diagnosis of "phyllodes tumor, uncertain behavior" or with an unclassified grade.

(2) Patients with a history of prior malignant tumor (excluding breast cancer) for whom the time from curative treatment to study enrollment is <5 years, or the expected disease-free survival is <5 years, or who have other concurrent diseases that may affect the assessment of study endpoints.

(3) Patients lost to follow-up or with missing critical data (e.g., pathological grade, surgical procedure, follow-up outcomes).

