## 1. Abstract (Brief Summary)

This is a national, multicenter, retrospective cohort study based on real-world data from approximately 3,500 patients with breast phyllodes tumor (PT) diagnosed between 2001 and 2023 across 8 tertiary hospitals in China. The study aims to systematically describe the clinicopathological characteristics, treatment patterns, and long-term prognosis of Chinese PT patients. The primary outcomes are local recurrence (LR), distant metastasis (DM), and overall survival (OS). Secondary outcomes include disease characteristics and current treatment practices. This study will provide Chinese population evidence to support personalized treatment and guideline updates.

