#### **2.2.4 Prognostic Factors**

Domestic and international studies consistently agree that WHO histological grade (benign, borderline, malignant) is the most important prognostic factor. Higher grade is associated with greater risks of recurrence and metastasis. In addition, margin status, stromal overgrowth, tumor size, and patient age have also been identified as key factors affecting local recurrence [18-20]. Sun Yat-sen Memorial Hospital, Sun Yat-sen University, previously developed and validated a nomogram based on clinical and pathological factors from 334 PT cases using Cox regression to assist in evaluating PT prognosis, with external validation [21]. Benign PT does not significantly affect overall survival, so survival-related prognostic models mainly focus on borderline and malignant PT [9,22].

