### **3. Study Objectives and Endpoints**

#### **3.1 Objectives**

##### **3.1.1 Primary Objective**

To systematically elucidate the survival and prognostic characteristics of Chinese patients with breast phyllodes tumor (PT) using 20-year real-world data from a national multicenter cohort.

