### **(5) Bias control (as described in 5.3) – PSM, IPTW, E-value.**

### **(6) Stratified, subgroup, and sensitivity analyses**

- **Stratified analysis:** All primary analyses will be stratified by pathological grade (benign/borderline/malignant) to compare prognostic factors across grades.
- **Pre-specified subgroups:** Age (<35 vs. ≥35 years), tumor size (<5 cm vs. ≥5 cm), surgical procedure (segmental resection vs. minimally invasive rotary

excision, wide local excision vs. total mastectomy). Forest plots will display subgroup HRs with interaction P-values.

- **Sensitivity analyses:**
  - Complete case analysis vs. multiple imputation.
  - Varying PSM parameters (1:1 vs. 1:2 matching, caliper 0.1 vs. 0.2).
  - Separate analysis of recurrence definitions (ipsilateral chest wall/axilla only) to exclude misclassification.
  - Excluding patients with follow-up <6 months.
  - For OS, competing risk analysis with death from PT vs. other causes.

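### The undefined concurrent-disease exclusion in 4.2(2) can screen out patients at higher risk of other-cause death, although OS is a primary all-cause endpoint; define it narrowly and keep it out of the OS analysis

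*Combined protocol and SAP*

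**What the plan says.** Exclusion criterion (2) in section 4.2 begins with patients who have a prior non-breast malignancy. It sets two 5-year conditions for them and then adds "or who have other concurrent diseases that may affect the assessment of study endpoints". Nothing says which diseases count, how severe they must be, when they must be present, or who decides.

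OS is one of three primary outcomes (section 1). Section 3.2.1(9) measures it "from the date of initial surgery to the date of death from any cause". The primary objective (3.1.1) is to describe survival and prognosis in Chinese PT patients from real-world data.

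Three other places bear on the point:
- Section 2.2.4 states: "Benign PT does not significantly affect overall survival". Section 5.4.1 expects a benign:borderline:malignant split of about 7:2:1, and 5.4.2(6) stratifies all primary analyses by grade.
- Section 5.4.2(2) treats death as a competing event for LR and DM, and 5.4.2(6) adds a sensitivity analysis: "For OS, competing risk analysis with death from PT vs. other causes".
- Section 5.3(3) relies on strict criteria to limit selection bias and says: "All eligible consecutive cases will be enrolled; no sampling based on outcome or exposure".

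**The concern.** For an endpoint that counts every death, a disease that bears on the endpoint can be read as one that raises mortality. A site reading the clause that way could remove patients with, say, heart failure, cirrhosis or renal failure. Those patients would contribute a disproportionate share of other-cause deaths.

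The benign stratum is the most exposed in relative terms. If benign PT has little effect on survival, its deaths are mainly from other causes, and those are the deaths the clause could filter out. Benign-stratum OS would then describe a healthier subset than the patients named in the objective.

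The open wording adds two practical risks. Eight centres may apply it differently. The word concurrent is also not tied to initial surgery, so disease arising during follow-up might be counted. The blinding in section 6.2.4 covers data entry, not eligibility, so charts could be screened with the outcome in view.

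**Working it through.** **The plan's own figures.** The only event count in the design is for LR (5.4.1). It reproduces: 3,500 × 0.11 = 385. From the grade-specific rates in 2.1, 0.7 × 7.1% + 0.2 × 16.7% + 0.1 × 25.1% = 10.82%, and 3,500 × 10.82% = 379. Both agree with about 380. This does not bear on OS. The documents give no OS rate, no number of deaths and no share of patients expected to fall under the clause.

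**Formula.** At a fixed time, let f be the share of otherwise eligible patients removed by the clause.
- S_full = (1 − f) × S_included + f × S_excluded
- Overstatement = S_included − S_full = f × (S_included − S_excluded)

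This is positive whenever the excluded patients survive less well, and zero if they survive equally well.

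**Illustration, benign stratum (0.7 × 3,500 = 2,450, taken as the number before the clause is applied).** All inputs below are assumptions: 10-year mortality 1.5% in included patients, 15% or 30% in excluded patients, and f of 1% or 5%.

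| f | Mortality in excluded | Full-stratum mortality | OS overstated by | Share of true mortality missed |
|---|---|---|---|---|
| 1% | 15% | 0.99 × 1.5 + 0.01 × 15 = 1.635% | 0.135 points | 0.135/1.635 = 8% |
| 1% | 30% | 0.99 × 1.5 + 0.01 × 30 = 1.785% | 0.285 points | 0.285/1.785 = 16% |
| 5% | 15% | 0.95 × 1.5 + 0.05 × 15 = 2.175% | 0.675 points | 0.675/2.175 = 31% |
| 5% | 30% | 0.95 × 1.5 + 0.05 × 30 = 2.925% | 1.425 points | 1.425/2.925 = 49% |

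At f = 5%, expected deaths are 2,450 × 2.175% = 53 to 2,450 × 2.925% = 72 in the full stratum. Among included patients they are 2,450 × 0.95 × 1.5% = 35.

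**Illustration, whole cohort.** Assume 10-year OS of 95% in included patients. With f from 1% to 10% and OS of 85% down to 50% in excluded patients, the overstatement runs from 0.01 × 10 = 0.1 to 0.10 × 45 = 4.5 points. At f = 5% and 70% OS in excluded patients it is 0.05 × 25 = 1.25 points, and the clause removes (0.05 × 30%)/6.25% = 24% of all deaths.

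**Does anything in the plan offset this?** The competing-risk models for LR and DM and the cause-of-death analysis for OS use included patients only. No sensitivity analysis restores excluded patients. Sections 3.2.2 and 3.2.3 list history of other malignancy but no general comorbidity. The eCRF (6.1.1) mentions medical history without specifying a comorbidity covariate.

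**The case against.** The strongest objection concerns what the clause means. Grammatically it can attach to patients with a prior malignancy, which would make it reach only a small group. It also speaks of diseases that affect the assessment of endpoints. Heart failure does not make it harder to establish that a patient died, so the wording may be aimed at diseases that obscure whether a lesion is PT recurrence or metastasis. The planned analyses of other-cause death show that the authors expect such deaths in the cohort. Both narrow readings are tenable and either would shrink the effect. The text does not settle the matter, so the effect is conditional on how sites read the clause.

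The absolute effect may also be small. Everyone included had surgery, and section 2.2.2 describes Asian patients as often young, so serious comorbidity may be uncommon. This stands. The relative loss of deaths can still be material where deaths are few.

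A reader might infer that the clause contradicts the promise of consecutive enrolment. It does not: section 5.3(3) refers to eligible cases, that is, after exclusions. The tension is with the strict definitions promised there and with the real-world survival aim.

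A reader might also infer that the clause should simply be deleted. That would discard a legitimate use, since some diseases could make LR or DM impossible to attribute to PT.

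**Conclusion.** The clause needs to be defined, and it should not operate on OS. To the extent that it is applied to life-limiting comorbidity, it pushes reported OS upward and lowers the other-cause mortality seen in the competing-risk analyses. Nothing in the plan corrects for this.

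The direction of the clause's own effect follows from the formula once excluded patients are taken to survive less well. The size rests wholly on assumed inputs: about 0.14–1.4 points of 10-year OS in the benign stratum, equivalent to 8–49% of that stratum's mortality. The relative figures look large only because the assumed baseline mortality is low.

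A reader might infer that the plan's reported OS will be too high overall. The documents do not support that. Criterion 4.2(3) excludes patients lost to follow-up, whom the OS definition would allow to be censored, and that may move OS the other way. The net bias is undetermined. Nor do the documents allow a calculation of any distortion in the effect of age on OS.

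**What to change.** - Do not exclude patients from the cohort or from the OS analysis for concurrent non-malignant disease.
- Restrict the clause to diseases, known at initial surgery, that prevent LR or DM from being attributed to PT, and apply it only to the LR and DM analyses.
- State whether the clause extends beyond patients with prior malignancy.
- Report the number excluded under it by centre and grade.
- Record major comorbidity at initial surgery from HIS, already a data source under 6.1.2, and use it as a covariate where available. The planned competing-risk and cause-of-death analyses then handle other-cause death.

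The cost is a reworded criterion and some retrospective extraction across eight centres and records from 2001 to 2023, where comorbidity may be recorded unevenly. Reported OS would probably become slightly less favourable. The change should be made before case selection and database lock.
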